15.2 Analysis of Secondary Endpoints

Summary statistics (including number, mean, median, standard deviation, minimum and maximum for a continuous variable, or % at each level for a categorical variable) of each secondary endpoint, will be calculated by treatment and period.

Mean blood ketone levels at month 3: Mean blood ketone levels at month 3 will be calculated as average of all fingerstick BHB levels from day 0 to 90. Mean blood ketones levels will be analyzed using a linear regression model with treatment (BGM or CGM) as the effect variable.

Change in other CGM-derived metrics and A1c: These metrics include percent (%) of time with glucose above 180 mg/dL, above 250 mg/dL, below 70 mg/dL, and below 54 mg/dL based on 14-day CGM during Baseline (period A) and Post-Dietary Change (period B). These metrics also include measures of mean and variation in glucose profiles: mean glucose, % coefficient of variation, mean amplitude of glucose excursion (MAGE) based on 14-day CGM during Baseline (period A) and Post-Dietary Change (period B). Change in A1c during Baseline and Post-Dietary Change period is also included and evaluated here.

All secondary endpoints will be analyzed using linear mixed models with treatment (BGM or CGM), period (Baseline (period A) and Post-Dietary Change (period B)), and interaction between treatment and period as fixed effects, and patient as random effect. Analyses of such models are similar to the analysis for the primary endpoint.

Reaching CGM-derived consensus targets at month 3: This includes percent (%) of time with glucose >250 mg/dL <5% (yes/no); percent (%) of time in glucose >180 mg/dL <25% (yes/no); percent (%) of time in glucose 70-180 >70% (yes/no); percent (%) of time in glucose <70 mg/dL <4% (yes/no); percent (%) of time in glucose <54 mg/dL <1% (yes/no); percent (%) of time in glucose 70-180 AND percent (%) of time in glucose <70 mg/dL <4% (yes/no); percent (%) of time in glucose 70-180 AND percent (%) of time in glucose <54 mg/dL <1% (yes/no) based on 14-day at Post-Dietary Change (period B).

Since each endpoint is a dichotomous variable indicating if a patient reaches the consensus target goal at month 3 (yes/no), they will be analyzed using logistic regression models with treatment (BGM or CGM) as the effect variable.

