4.1 Study Objectives

The primary objective of this study is to compare the difference in change in 14-day CGM-derived TIR (% time with glucose 70-180 mg/dL) during Baseline and 3-month Post-Dietary Change periods between participants with T2D who are randomized to use either BGM or CGM to guide dietary and diabetes medication adjustments as part of the Virta Treatment.

The secondary objectives of this study are to compare:

1. Difference in 90-day mean blood ketone levels between BGM and CGM arms
2. Difference in changes in other CGM-derived metrics from Baseline to 3-month Post-Dietary Change period between BGM and CGM arms
3. Difference in percent of participants reaching CGM-derived consensus targets at the end of the 3-month Post-Dietary Change period between BGM and CGM arms
4. Difference in Change in HbA1c from Baseline to the end of the 3-month Post-Dietary Change period between BGM and CGM arms

The exploratory objectives of this study are to describe:

1. Change in CGM-derived TIR during Baseline and 6-month Follow-Up period
2. Change in other CGM-derived metrics during Baseline and 6-month Follow-Up period
3. Percent reaching CGM-derived consensus targets during 6-month Follow-Up period
4. Change in A1c from Baseline to 6-month Follow-Up period
5. Change in diabetes medication use
6. Change in dietary intake
7. Change in body mass index (BMI) and body weight
8. Percent reaching blood ketone targets $\geq 0.5\text{mM}$
9. Mean blood ketone levels
10. Change in CGM-derived ‘time in tight range’ (TITR; glucose 70-140 mg/dL)
11. Absolute values in CGM-derived metrics
12. Number of contacts between participants and Virta care team
13. Change in mean scores on patient-reported outcome (PRO) surveys

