4.2.2 Secondary Outcome Measures

Outcome	Assessment Method
1. Mean of all blood ketone levels from day 0 to day 90	BHB levels as tested by Precision Xtra Blood Glucose & Ketone Monitoring System; ketones requested twice daily throughout study
2. Change in other CGM-derived metrics from Baseline to 3-month Post-Dietary Change period: 
 Time above range >180 mg/dL Time above range >250 mg/dL Time below range <70 mg/dL Time below range <54 mg/dL Mean sensor glucose % Coefficient of variation Mean amplitude of glucose excursion 	See CGM-related outcome measures described above
3. Reaching CGM-derived consensus targets in the 3-month Post-Dietary Change period (yes/no): 
 Time >250 mg/dL <5% Time >180 mg/dL <25% Time 70-180 mg/dL >70% Time <70 mg/dL <4% Time range <54 mg/dL <1% Time 70-180 mg/dL >70% AND Time <70 mg/dL <4% 	See CGM-related outcome measures described above

 ● Time 70-180 mg/dL >70% AND Time <54 mg/dL <1% 	
4. Change in HbA1c from Baseline to 3-month Post-Dietary Change period	HbA1c assessed at Virta-approved, CLIA-certified laboratory using NGSP HbA1c method

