8.2 Baseline Assessments

After signing the ICF, demographic and anthropometric information will be assessed to describe the participants. Age at enrollment, race, ethnicity, income, education, marital status, year of type 2 diagnosis, gender identity, biological sex, weight, height, etc. will be collected at baseline.

Baseline assessments also include a 14-day, blinded CGM assessment using the FreeStyle Libre Pro system. The FreeStyle Libre Pro system (sensor and reader) is commercially available and will be used according to user manual instructions; however, the system will be started at home by the participant instead of in a clinic with an HCP. The sensor will be returned to the clinical site for data download. A minimum of five days of blinded Libre Pro CGM sensor data must be obtained for randomization. Participants will use the provided reader to confirm adequate days of data recording during the Baseline assessment period.

All 14-day, blinded, FreeStyle Libre Pro sensors will be returned via mail. Data will be uploaded with a FreeStyle Libre Pro reader using the Libre 2 algorithm and then downloaded to secure study computer. Blinded FreeStyle Libre Pro sensors will be tracked by linking sensor serial numbers with study participant ID numbers.

Once baseline assessments are complete, the study intervention (use of CGM vs. BGM) begins concurrently with the initiation of the WFKD (Day 0).

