15.1 Analysis of Primary Endpoint

Summary statistics (including number, mean, median, standard deviation, minimum and maximum) for percentage (%) of TIR (glucose 70 - 180 mg/dL), based on 14-day CGM assessments, will be calculated by treatment and period.

The primary endpoint will be analyzed using a linear mixed model with treatment (BGM or CGM), period (Baseline (period A) and Post-Dietary Change (period B)), and interaction between treatment and period as fixed effects, and patient as random effect. The model will be fitted to all the data simultaneously and from this model the relevant treatment differences will be estimated. Adjusted mean estimates for each treatment with standard errors, the adjusted estimate of treatment mean difference with standard error and a 95 % confidence interval for the treatment mean difference will be provided. The statistical test will be two-sided tests at a nominal 5% significance level.

Enrolled participants without adequate Baseline blinded Libre Pro CGM data will not be included in the analysis. Adequate Baseline blinded CGM data is defined as a minimum of 5 days of sensor data. In cases where two blinded sensors are worn in the same contact period, sensor data may be combined.

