15.5 Sample Size Determination

The sample size estimation is based on the following assumptions:

- 80% power (at 0.05 significance level) to test the primary hypothesis, which is the difference in TIR between BGM and CGM arms
- anticipated mean difference in TIR between CGM and BGM = 10%
- anticipated standard deviation of TIR in each arm = 20%

The two-sided t-test suggests N=63 for each arm. Assuming an 85% retention rate at the end of the 3-month Post-Dietary Change period brings the required sample size to approximately N=75 per arm; or N=150 randomized participants with adequate Baseline data.

Consented participants who are not randomized do not count toward the 150 total participants; these participants may be replaced.

16 Ethics/Protection of Human Subjects

This protocol and any amendments will be submitted to Advarra for formal approval of the study conduct. The decision of the IRB concerning the conduct of the study will be made in writing to the Investigator. A copy of the initial IRB approval letter will be provided to the study funder (Abbott Diabetes Care) before commencement of this study.

This study will be conducted in full accordance with all applicable Federal and state laws and regulations including 45 CFR, and the HIPAA Privacy Rule. Any episodes of non-compliance will be documented. The Investigators will perform the study in accordance with this protocol, will obtain consent, and will report unexpected problems in accordance with IRB policies and procedures. Collection, recording, and reporting of data will be accurate and will ensure the privacy, health, and welfare of research participants during and after the study.

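### The Month 3 target-attainment models in Section 15.2 leave out the baseline CGM value, and both composite targets there lack the >70% cut-off

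*Combined protocol and SAP*

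**What the plan says.** Section 15.2 lists seven yes/no targets at Month 3: five single and two composite. It builds them from Post-Dietary Change data and states that "they will be analyzed using logistic regression models with treatment (BGM or CGM) as the effect variable". No covariate is named for them there or elsewhere. The matching objective in Section 4.1 is worded as "Difference in percent of participants reaching CGM-derived consensus targets".

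Baseline CGM data should be at hand for nearly everyone. Section 8.2 says: "A minimum of five days of blinded Libre Pro CGM sensor data must be obtained for randomization". Section 15.1 adds, for the primary analysis: "Enrolled participants without adequate Baseline blinded Libre Pro CGM data will not be included in the analysis". The mixed models for TIR, the other continuous CGM metrics and HbA1c already use the baseline period.

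The composites appear in Section 15.2 as "percent (%) of time in glucose 70-180 AND percent (%) of time in glucose <70 mg/dL <4% (yes/no") and "percent (%) of time in glucose 70-180 AND percent (%) of time in glucose <54 mg/dL <1% (yes/no"). Neither puts a threshold on the 70-180 part. Section 4.2.2 does, for example "Time 70-180 mg/dL >70% AND Time <70 mg/dL <4" (percent). Section 4.2.3 repeats the cut-off for Month 6, and 15.2 itself attaches it to the single TIR target.

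**The concern.** There are three linked points.

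1. **Precision.** A participant's baseline value of a CGM metric is a natural predictor of whether the matching target is met three months later. Omitting it does not bias a randomized comparison. It does leave between-participant variation in the error that data already collected could remove, and it makes no allowance for chance imbalance at baseline.
2. **Scale.** The treatment effect in a logistic model is an odds ratio. The objective is a difference in percentages, and 15.2 plans no confidence interval for that difference.
3. **Composite definition.** A percentage of time without a threshold cannot form half of a yes/no rule. Read literally, each composite reduces to the time-below-range target already in the list, so two of the seven endpoints would duplicate others.

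At stake is the width of the intervals on a set of secondary endpoints and the correct programming of two of them.

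**Working it through.** **The plan's own figure.** Section 15.5 assumes a 10-point difference in TIR, "anticipated standard deviation of TIR in each arm = 20" (percent), 80% power and two-sided 5%. By the normal formula, n = 2 × (1.960 + 0.842)² × 20² / 10² = 62.8, so 63 per arm. With 85% retention, 63 / 0.85 = 74.1, so 75 per arm. Both stated figures reproduce. The plan gives no power for the target endpoints.

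**Inputs for the check.** From Section 15.5: 63 per arm, SD 20, 10-point difference. From Section 4.2.2: cut-off 70. Assumed, because the documents give neither: Month 3 arm means (55 v 65 up to 75 v 85) and a baseline to Month 3 correlation of 0, 0.3, 0.5 or 0.7, equal in both arms.

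**Unadjusted comparison.** With normal TIR, attainment is p = 1 − Φ((70 − mean)/20). At 65 v 75 this is 40.1% v 59.9%. The 95% CI half-width for the difference is 1.96 × √(0.401 × 0.599/63 + 0.599 × 0.401/63) = 17.1 points; the average over simulated trials was 17.0. Across the five pairs of means and the three tests below, unadjusted power is 54-65%.

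**Adjusted comparison.** Fit logit P(target met) = a + b × treatment + c × baseline TIR. Predict each participant's probability under CGM (p1) and under BGM (p0). The standardised difference in percent is the mean of p1 − p0, with its variance taken from the influence function (divisor N − 3).

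Results from 10,000 simulated trials per cell:

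| Correlation | Power change, standardised difference (points) | Power change, range over Wald, likelihood-ratio and standardised difference (points) | Fall in variance | Equivalent extra participants | Half-width at 65 v 75 (points; unadjusted 17.0) |
|---|---|---|---|---|---|
| 0 | -2 to -1 | -3 to +2 | about 0% | about 0% | 17.1 |
| 0.3 | 0 to +2 | -1 to +4 | 4-5% | about 5% | 16.6 |
| 0.5 | +5 to +6 | +5 to +9 | 14-16% | 16-19% | 15.7 |
| 0.7 | +14 to +16 | +14 to +18 | about 30% | about 44% | 14.2 |

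Extra participants are 1/(variance ratio) − 1; for example, 1/0.840 − 1 = 19% and 1/0.695 − 1 = 44%. Clipping TIR to 0-100 gave much the same power changes for the standardised difference (-2.2 to -0.4, -0.2 to +1.6, +4.4 to +6.4 and +13.7 to +15.5).

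**Error rates.** With no treatment effect, the standardised difference rejects in 4.8-5.8% of trials and the unadjusted difference in 5.2-6.0%. Coverage of the adjusted interval is 94-95%.

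**Targets that most participants meet.** At correlation 0.5 the variance falls 8% at 90% attainment and 4% at 95%. The chance that at least one arm has no failures is 1 − (1 − p⁶³)²: 0.3% at p = 90%, 7.7% at 95% and 48% at 98% (assumed rates). With 63/63 v 57/63, the likelihood-ratio p is 0.003 and Fisher's exact p is 0.028. The difference is 6/63 = 9.5 points, with a Newcombe hybrid score interval of 1.8 to 19.3.

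**Composites, illustration only.** Suppose TIR attainment is 40% v 60%, and 95% in each arm meet the time-below-range target independently of it. With the cut-off the composite is 0.40 × 0.95 = 38% v 0.60 × 0.95 = 57%. Without it, it is 95% v 95%.

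**The case against.** The strongest reply is that a valid analysis is being faulted for not being the most efficient one. The treatment-only model holds its type I error, only the primary hypothesis is powered, and nothing in the plan is unworkable. That stands, and it is why the point is minor.

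The gain also depends on an unknown correlation. Between the two recordings participants start a ketogenic diet, medications are titrated and the CGM arm changes device, so a high correlation cannot be presumed. It may also differ by arm: with 0.5 in one arm and 0.1 in the other, the variance falls by only about 3-6%. So the case is for a modest and conditional gain.

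A treatment-only logistic model reproduces the two arm percentages exactly, and 15.2 already promises percentages by treatment. What is missing is a confidence interval for their difference, not the percentages themselves.

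A few randomized participants may lack a usable baseline value. The five days are confirmed by the participant before the sensor is mailed back, and the exclusion is written in 15.1 only. The adjusted model therefore needs a stated rule for this.

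Finally, a programmer who consults 4.2.2 will build the composites correctly. That is likely, but it does not justify leaving the analysis section wrong.

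**Conclusion.** The point holds, as a worthwhile improvement and not a flaw that threatens the trial. The target-attainment models use no baseline information although it is collected as a condition of randomization, and the effect they estimate is not on the scale of the objective. For TIR >70% at 63 per arm, the standardised, baseline-adjusted difference costs about 1-2 points of power if the correlation is 0 and gains 14-16 if it is 0.7. At 0.5 the 95% CI half-width at 65 v 75 falls from 17.0 to 15.7 points. These sizes rest on the plan's SD and difference, on assumed means, and on a common correlation in both arms. Targets met by 90% or more gain little. The missing cut-off in the composites is a plain textual inconsistency that needs no assumption, and the intended rule can be recovered from 4.2.2.

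**What to change.** In Section 15.2, before the data are analysed:

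1. State that each logistic model includes treatment and the continuous baseline value of the corresponding CGM metric, with baseline TIR for the two composites. Make the standardised difference in percent reaching target, with a 95% CI from the influence-function variance, the main estimate, and the odds ratio supportive. The adjusted odds ratio is conditional on baseline and differs from the unadjusted one, so it should not lead.
2. State how a missing or inadequate baseline value is handled, for example by extending the rule in 15.1 to these endpoints.
3. Restore >70% after the 70-180 range in both composites, to match 4.2.2.

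Two optional tidy-ups: limit the sentence assigning mixed models to all secondary endpoints to the change metrics and HbA1c; and state that if everyone or no one in an arm meets a target, Fisher's exact test and a difference in percent with a named score interval (such as Newcombe's) replace the odds ratio.

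The cost is SAP wording and a few lines of code, with no new data. If baseline and Month 3 values are uncorrelated, adjustment gains nothing and can cost up to about 3 points of power, depending on the test.

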15.3 Analysis of Exploratory Endpoints

Analysis of exploratory endpoints is descriptive (including number, mean, median, standard deviation, minimum and maximum for a continuous variable, or % at each level for a categorical variable). A 95% confidence interval (CI) will be calculated for each endpoint, but no hypothesis testing or inferential analysis will be conducted due to the exploratory nature of these variables.

15.4 Study Hypotheses

Alternative primary hypothesis: CGM will lead to greater improvements in TIR at month three compared to BGM in people with T2D who participate in the Virta Treatment.

Alternative secondary hypotheses:

- CGM will lead to greater blood ketone levels at month three (a presumed marker of adherence to the Virta dietary plan) compared to BGM in people with T2D who participate in the Virta Treatment.
- CGM will lead to greater improvements in other glycemic markers at month three compared to BGM in people with T2D who participate in the Virta Treatment.

15.5 Sample Size Determination

The sample size estimation is based on the following assumptions:

- 80% power (at 0.05 significance level) to test the primary hypothesis, which is the difference in TIR between BGM and CGM arms
- anticipated mean difference in TIR between CGM and BGM = 10%
- anticipated standard deviation of TIR in each arm = 20%

The two-sided t-test suggests N=63 for each arm. Assuming an 85% retention rate at the end of the 3-month Post-Dietary Change period brings the required sample size to approximately N=75 per arm; or N=150 randomized participants with adequate Baseline data.

Consented participants who are not randomized do not count toward the 150 total participants; these participants may be replaced.

16 Ethics/Protection of Human Subjects

This protocol and any amendments will be submitted to Advarra for formal approval of the study conduct. The decision of the IRB concerning the conduct of the study will be made in writing to the Investigator. A copy of the initial IRB approval letter will be provided to the study funder (Abbott Diabetes Care) before commencement of this study.

This study will be conducted in full accordance with all applicable Federal and state laws and regulations including 45 CFR, and the HIPAA Privacy Rule. Any episodes of non-compliance will be documented. The Investigators will perform the study in accordance with this protocol, will obtain consent, and will report unexpected problems in accordance with IRB policies and procedures. Collection, recording, and reporting of data will be accurate and will ensure the privacy, health, and welfare of research participants during and after the study.

16.1 Informed Consent and HIPAA Authorization

Interested participants will be asked to electronically sign a combined ICF and HIPAA authorization form that will be sent to participants from Virta staff via DocuSign. Participants will be enrolled in the study after signing the ICF. The ICF will describe the purpose of the study, the procedures to be followed, and the risks and benefits of participation. A copy of the informed consent and HIPAA authorization will be emailed to each participant.

16.2 Conflict of Interest

Study personnel from Virta Health have been offered stock options in Virta Health and therefore have the potential for a significant financial interest in the company. The intervention being tested in the present investigation, however, is the utilization of a commercially available continuous glucose monitor from Abbott Diabetes Care, to which Virta Health study personnel have no conflict. The ICF and any publications resulting from this study will reflect these potential perceived conflicts of interest.

[figure not shown]
17 Appendices

Appendix A. Study Schematic

Appendix B. Study Periods and Assessments

Appendix C. Participant-Facing Materials

17.1 Appendix A. Study Schematic

17.2 Appendix B. Study Periods and Assessments

CGM vs. BGM to Optimize Glycemic Outcomes in T2D Following the Virta Treatment Ver. 2.0 06Dec2022

Study Period	Baseline	Diet Change	Post-Dietary Change / Intervention			Follow-Up
			30 to 44 +/-10	60 to 74 +/-10	90 to 104 +/-10	
Study Day	-21 to -1	0				
Assessment (Contact #)	Baseline Assessment (Contact 1)		Month 1 Assessment (Contact 2)	Month 2 Assessment (Contact 3)	Month 3 Assessment (Contact 4)	Month 6 Assessment (Contact 5)
Demographic Data	X					
14-Day Baseline Blinded CGM	X					
Personal Libre 2 CGM Use (CGM arm only)		←		X	→	
14-Day CGM Data Download (CGM arm only)			X	X	X	X
14-Day Blinded CGM Wear & Data Download (BGM arm only)			X	X	X	X
Ketones 2x/Day		←		X	→	
HbA1c	X				X	X
Medication Use	X		X	X	X	X
ASA-24 (single recall)	X		X	X	X	X
Height	X					
Weight/BMI	X		X	X	X	X
Diabetes Distress Survey	X				X	X
Lifestyle Change Survey					X	X
CGM Satisfaction Survey (CGM arm only)					X	
Participant Contacts with Virta			X	X	X	X
Adverse Events		←		X	→	

